Sample Size. We estimated our sample requirements using power analyses for primary aims to characterize the reduction in toxic exposure of cigarette smokers randomized to the e-cigarette group compared to cigarette smokers randomized to assessment-only controls (Aim 1:H1) from baseline to week 6 will be significantly lower in the EC group compared to the assessment-only group. Empirical power estimates were assessed by generating multivariate random samples that were matched to the expected response patterns for smokers in control and switching arms with each condition using the same correlation structure of assessments over time as observed in a previous study. In the switching condition we expect larger effects ($d=-0.67$) on primary outcomes (NNAL) for the ~40% of smokers able to switch more completely relative to smokers partially switching ($d=-0.16$). With no change expected in control, we powered primary outcomes for end-of-treatment analyses using an average of effects given 30% of switching smokers with large and 70% with small effects. With a median effect of -0.37 ($SD=0.11$) across 1000 data sets, simulations revealed that the planned design would provide greater than 0.82 power for detecting the treatment differences with a sample of 180 subjects, with an allowance for up to 20% attrition. For Aim1: H2 we will have power to detect moderate effects of changes in cigarette consumption on change in toxicants. In published effects of differences in consumption levels on nitrosamines, 77 differences in consumption (20 vs 10 cig/day) reflected mean difference in log NNAL of $2.60-2.35=0.24$ and effect sizes with $d=0.48$ after 10 weeks 78. We estimate adequate power >0.80 given expected cigarette reductions. Changes in cognitive measures (Aim 2) including decreased perception of harm, average differences in utility of combustible and EC, and increased self-efficacy for quitting are expected to be moderately associated with EC use. Empirical power analyses using regression models of change in cognitive measures over 1000 simulated data sets support the ability to detect moderate effects ($d>0.30$) using a standardized difference in means of cognitive measures with power >0.80 .

V. Participant Screening and Enrollment

Prospective participants will be determined eligible or ineligible within 48 hours of initial contact. If eligible, the baseline visit will be scheduled, and a postcard reminder sent out. Screening will occur over the phone, in person, or with an online screening survey developed in REDCap.

Final eligibility is not decided until baseline visit, contingent on blood pressure under 160 (systolic) and 105 (diastolic), carbon monoxide over 5 PPM to validate smoking status, and researcher-assessed stability. Participants who do not meet criteria will not be included in the study and given a smoking cessation referral. San Diego ineligible participants will be referred to the California Smokers' Helpline and Kansas City ineligible participants will be referred to the Kansas Tobacco Quitline. Transportation will be provided to and from study visits when needed in San Diego.

A. Inclusion Criteria

- ≥ 21 years of age
- Smoked cigarettes on ≥ 25 of past 30 days
- Smoked ≥ 5 cigarettes per day on days that smoked
- Smoked cigarettes for ≥ 6 months
- Carbon monoxide > 5 PPM at baseline
- Blood pressure systolic or diastolic < 160/105
- Hispanic/Latinx at San Diego or Black/African American at Kansas City
- Fluent in English or Spanish
- Willing to switch from smoking cigarettes to e-cigarettes for 6 weeks
- Regular access to a telephone
- Transportation to attend Swope Health Central in next six weeks (Kansas City)

B. Exclusion Criteria

- Primary use of other tobacco products or equal use of cigarettes and other tobacco products
- E-cigarette use on ≥ 4 of the past 30 days
- Currently in a smoking cessation program or other clinical trial
- Use of nicotine replacement therapy or medicine which aids smoking cessation in the past 30 days
- Hospitalizations for a psychiatric issue in the past 30 days
- Heart-related event in the past 30 days. Examples include heart attack, stroke, severe angina (i.e. chest pain), ischemic heart disease, and vascular disease
- Planning to move out of San Diego or Kansas City in the next 6 weeks
- Another person in the household enrolled in the study
- Women: pregnant, breastfeeding, or planning to become pregnant in the next six months
- Screener judgment about unstable mental status or health status

VI. Study Design and Timeline

This study is a randomized controlled trial using a 2:1 study randomization ratio. The treatment group will receive an e-cigarette and nicotine pods for six weeks and are encouraged to make a complete switch from combustible cigarettes to e-cigarettes. The study will consist of three in-person visits (baseline, week 2, and week 6) in which measurements are conducted and behavioral support is provided to the e-cigarette group. Phone calls will be scheduled between the visits (week 1 and week 4) to confirm appointments, collect data on tobacco use, and to support switching to e-cigarettes (e-cigarette group only).

[figure not shown]

Figure 1. Study Timeline.

Informed Consent. The informed consent will be reviewed by having the researcher read the consent form out loud. The participant will be given time to read the informed consent form and ask questions. It will be made clear in the consent form that the participant has the option to take more time to consider their desire to participate in the study and reschedule at a later date, or to decline to participate at any point. The study begins once the participant signs the consent form, indicating understanding of the procedures, requirements, and consent.

Incentives. Participants will be compensated for their time during the lab visits at escalating increments of \$20 at baseline, \$40 at week 2, and \$60 at week 6, totaling up to \$120. Participants in the e-cigarette group are instructed that full compensation is contingent upon bringing back their used and unused pods to their next visit. At week 2 and week 6, \$20 of compensation is contingent upon bringing back pods. Those in the e-cigarette group have the opportunity to participate in a follow-up phone assessment six months after enrollment, entailing an additional \$20 compensation.

Study E-cigarettes. Participants in the e-cigarette group will be provided JUUL, a nicotine-salt based e-cigarette (see Figure 2). Participants will have the flavor selection of Virginia tobacco, cool mint, menthol, or mango pods containing .07 mL nicotine (5% nicotine). Pod use will be tracked using the Pod Count Form, requiring participants to bring to lab visits all used, unused, and partially used pods. Pods will be distributed based on cigarette use, and determined using the Pod Count Calculation Form. Education about switching will be verbally provided to the e-cigarette group. Participants will engage in motivational enhancement-based action planning and will receive JUUL usage instructions. Participants in the e-cigarette group will be provided a compatible wall adapter to ensure proper charging, a device carrying case, Q-tips to clean the device as needed, and a gallon Ziplock bag to store used pods.

Figure 2. JUUL electronic cigarette. Reprinted from *JUUL Labs, Inc*, Retrieved December 9, 2018, from www.juul.com. Copyright 2018.

VII. Participant Retention

Participant retention will be maintained by using a variety of contact methods including call, text, email, physical letter in the mail, and reaching out to emergency contacts. No more than six contact attempts, of various forms, will be made. Contacting emergency contacts and sending a letter will be the last efforts made to contact an unreachable participant. Additionally, participants will be sent postcards reminding them of the day and time of their next lab visit, and appointment reminder cards will be given out at the baseline and week 2 visit reminding about upcoming phone calls.

Lab visits will have pre-determined time windows. The week 2 visit can be scheduled up to one week before or after the originally scheduled date of two weeks after the baseline visit. The week 6 visit can be scheduled up to four weeks before or after the originally scheduled date of six weeks after the baseline visit. Ripple protocol details the scheduling protocol.

VIII. Laboratory Procedures and Sampling

Data from biological measurements and samples will be recorded on paper and/or in REDCap.

The table below shows the equipment used for the biological measures, and timepoints taken.

Measure	Equipment	Baseline	Week 2	Week 6
Carbon Monoxide	coVita Bedfont Micro+ Smokerlyzer®	X	X	X
Systolic Blood Pressure, Diastolic Blood Pressure, and Pulse	Omron® BP742N 5 Series Upper Arm Blood Pressure Monitor	X	X	X
Height	Health o meter® 500KL	X		

	Professional Digital Scale			
Weight	Health o meter® 500KL Professional Digital Scale	X		X
Spirometry: FVC, FEV1, FEV1/FVC%, PEF, and FEF25- 75%	Futuremed® Discovery-2™ Desktop Spirometer	X	X	X
Saliva (10 San Diego participants)	Saliva collection aid (straw): SB-WS No.61/524,096 Collection tube: Wheaton 1.8 mL yellow cap collection tube	X		X
Nasal Swab (20 Kansas City Participants)	Leukosorb tubes, Q-tips, saline	X		X
Urine	Dynarex Specimen Container 4oz. 118cc reorder No. 4253 Aliquots: Wheaton 20 ml disposable scintillation vials	X	X	X

Table 2. Biological measures, timepoints, and equipment for Project Switch.

CO measurement. Exhaled breath samples will be taken at all visits for carbon monoxide (CO), a by-product of smoke, using a Bedfont Micro+ Smokerlyzer. At baseline, CO measurement will be taken to confirm eligibility. A carbon monoxide level over 5ppm verifies smoking status. A carbon monoxide level 5ppm or lower at baseline makes a person ineligible to participate in the study. Participants will be allowed the opportunity to re-screen two weeks later.

Blood pressure. Systolic and diastolic blood pressure will be measured for screening purposes and throughout the study using a digital blood pressure cuff. If, at the baseline or week 2 visit, a participant's systolic blood pressure is greater than or equal to 160 mm Hg or their diastolic blood pressure is greater than or equal to 105 mm Hg, they will not be eligible to participate or continue participating in the study. Pulse will also be measured but not as an exclusion criteria. Participants who are ineligible at baseline due to uncontrolled blood pressure will be allowed the opportunity to re-screen two weeks later.

Height and weight. A medical scale will be used for a one-time measure of height. Weight will be measured at baseline and week 6 visit, with shoes removed.

Spirometry. Lung function will be measured at all lab visits using a Discovery-2 SpiroVision spirometer. At each session, participants will complete a minimum of three maneuvers (depending on the quality) consisting of a strong exhale and a strong inhale.

Participants will be given a mouthpiece at baseline that will be stored and used at subsequent visits. Participants will be given the option to manually hold their nose closed or to apply a nose clip.

Spirometer measures include: (1) forced vital capacity, FVC (2) Forced expiratory volume in one second, FEV1 (3) The percentage of the FVC expired in one second, FEV1/FVC% (4) peak expiratory flow, PEF (5) Forced expiratory flow over the middle one half of the FVC, FEF25-75%.

Saliva sampling. Saliva sampling is an exploratory addition to this study and will be taken from ten San Diego participants at baseline and week 6. The decision to take saliva sampling in San Diego resulted in an increase from the original $n=90$ to an $n=94$. Samples will be frozen and transported the testing facility on dry ice.

Nasal swab sampling. Nasal swab sampling is an exploratory addition to this study and will be taken from twenty Kansas City participants at baseline and week 6. The decision to take nasal swab sampling in Kansas City resulted in an increase of two participants for a final $n=92$. Samples will be frozen and transported the testing facility on dry ice.

Urine sampling. Urine will be collected at all lab visits and refrigerated until aliquoting. Participants will be instructed to provide at least half of the specimen cup of urine (about 60mL). Participants will be offered water at the beginning of lab sessions to help facilitate sampling.

Urine will be processed by aliquoting the sample into two smaller samples, each 15 mL. One sample will test for cotinine and need to be pre-treated with sodium bisulfate to obtain a pH between 2 and 3. The second sample will test for NNAL and will receive no additional treatment. Both samples will be frozen and stored at $-20\text{ }^{\circ}\text{C}$ before shipping with dry ice for testing.

A urine log will provide the following information for each urine sample: (1) participant ID (2) study time point (3) date: mm/dd/yyyy (4) testing for: NNAL or cotinine. Each lab visit will produce two samples stored for further testing.

Although urine will be taken at all three lab visits, only baseline and week 6 urine will be sent for testing. In the case of missing week 6 samples, week 2 samples will be sent instead as a method of imputation.

Sample shipment. Specimens will be transported in a leak-proof Styrofoam container in leak-proof secondary packaging, with absorbent material placed at the bottom and sides of the container for absorption. 10-15lbs dry ice will be used to maintain storage temperature during transport.

IX. Laboratory Analysis

Urine: cotinine ng/mL, creatinine mg/mL, nitrosamine 4-(methylnitrosamino)-1-(3-pyridyl)-1-butanol (NNAL) pg/mL, and 3-hydroxycotinine ng/mL

Saliva: Cytokine Panel and C-Reactive Protein

Nasal Swab: MMP9 ELISA in pg/mL and TGF-B1 ELISA in pg/mL

X. Study Visits Overview

Baseline	Week 1	Week 2	Week 4	Week 6
Participant consent	Follow-up check-in	Urine test	Follow-up check-in	Saliva sample (San Diego)
Saliva sample (San Diego)	Yesterday tobacco use	Blood pressure test (must be less than 160/105)	Yesterday tobacco use	Urine test
Complete contact sheet		Carbon monoxide test		Blood pressure test
Blood pressure test (must be less than 160/105)		Eligibility check		Carbon monoxide test
Carbon monoxide test (must be greater than 5 ppm)		Follow-up check in sheet (EC group)		Nasal swab (Kansas City)
Nasal swab (Kansas City)		Timeline follow back		Weight
Final eligibility check and Study ID assignment		Spirometry test		Follow-up check in sheet (EC group)
Randomization		Week 2 survey		Timeline follow back
Charge JUUL (EC group)		Collect used JUUL pods (EC group)		Spirometry test
Timeline follow back		Provide more JUUL pods (EC group)		Week 6 survey
Pod count form (EC group)		Schedule visits/phone calls		Collect used JUUL pods (EC group)
Height and weight		Compensation		Tobacco cessation referral
Baseline survey part 1				Exit survey
Spirometry test				Compensation
Baseline survey part 2				
Cigarette questions and breathing conditions				
E-cigarette switching fact sheet (EC group)				
E-cigarette use instructions (EC group)				
E-cigarette trial and subjective effects questionnaire (EC group)				

Baseline action planning (EC group)				
Schedule visits/phone calls				
Reimbursement schedule				
Urine test				
Compensation				

Table 3. Surveys and tests by study timepoint.

At each lab visit, participants will receive compensation and sign a receipt. At the end of the study, participants will be given a referral to the California Smokers' Helpline ([name]) or Kansas Tobacco Quitline ([name]).

XI. Study Questionnaires

Surveys will contain items on demographics, smoking measures, tobacco measures, physiological measures, and psychosocial assessments. Given the possibility of low literacy among participants, surveys will be verbally administered along with visual cue cards.

XII. Data Management

Missing data will be minimized through extensive training of research staff in addition to follow-up with participants. Data will be entered into REDcap electronically and paper forms (biological measures and pod count forms) will be stored in participant files. Paper forms with identifiable information such as consent and contact information will be stored in a separate, locked location. TLFB data will be entered into excel, with paper calendars and data entry forms stored in participant files. REDcap entry will happen after the lab session and will be audited and checked by project managers daily. REDCap is a secure, HIPAA-compliant, web-based application designed to support data capture for research studies. All protocol-specified data will be linked by unique subject ID, assigned at randomization. Paper files will be stored on site in a locked filing cabinet and any forms with identifying information (consent form and contact sheet) will be kept in a separate location. Data is only accessible to personnel involved with this research. Access is limited by the research facility being locked at all times.

XIII. Recording and Reporting of Adverse Effects

Development of any adverse effects will be monitored closely by a project manager such that fields capturing adverse events will be reviewed daily. At each study visit, participants will be asked about the development of any other, new, or worsening symptoms. At each visit and each phone call after the initial visit, participants in the e-cigarette condition will be asked if they were experiencing any barriers to switching to e-cigarettes or any concerns about switching. This open-ended format is intended to capture any unexpected adverse events. Unexpected serious adverse events will be reported to the CSUSM IRB and assessed by the PI to determine if related to e-cigarette use, and if so, reported to the NIH and FDA. Participants will be encouraged to contact staff if they have any questions, problems using their e-cigarette, or if any adverse events develop.

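### The reported median effect of -0.37 does not follow from the stated 30%/70% switching mix, which averages -0.313, so it is unclear which switching rate the power claim covers

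*Protocol*

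**What the plan says.** All the inputs stand in the Sample Size paragraph of the Protocol, just before Section V.

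- Expected effects in the switching arm: "we expect larger effects ($d=-0.67$) on primary outcomes (NNAL) for the ~40% of smokers able to switch more completely". The sentence continues with the second group: "able to switch more completely relative to smokers partially switching ($d=-0.16".
- Control arm and timing: "With no change expected in control, we powered primary outcomes for end-of-treatment analyses".
- Mix used for powering: "using an average of effects given 30% of switching smokers with large and 70% with small effects".
- Result: "With a median effect of -0.37 ($SD=0.11$) across 1000 data sets, simulations revealed that the planned design would provide greater than 0.82 power". The claim is made "with a sample of 180 subjects, with an allowance for up to 20% attrition".

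Section VIII later adds a few participants for exploratory sampling. San Diego's saliva sampling "resulted in an increase from the original $n=90$ to an $n=94", and Kansas City's nasal swabs "resulted in an increase of two participants for a final $n=92".

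**The concern.** The paragraph gives two component effects, the weights for averaging them and the simulated median that should result. The median is visibly larger than the weighted average. It agrees instead with a different weight, the share of about 40% mentioned one sentence before the 30% said to have been used.

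This calculation is the justification for 180 subjects on the primary hypothesis (Aim 1, Hypothesis 1). The proportion of smokers who switch more completely is a main uncertainty in it. If the power figure belongs to 30%, the design has some margin below the expected 40%. If it belongs to about 40%, that margin is not there. As written, a reader cannot tell which.

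**Working it through.** **Inputs from the Protocol.** Large effect -0.67; small effect -0.16; control effect 0; weights 30/70; expected share about 40%; reported median -0.37 with SD 0.11 over 1000 data sets; N=180 at 2:1; attrition up to 20%; power above 0.82.

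**Step 1: try to reproduce the median effect.** With both d values measured against an unchanged control:

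- 30/70: 0.30×0.67 + 0.70×0.16 = 0.201 + 0.112 = 0.313. Rounding of the inputs allows 0.308 to 0.318.
- 40/60: 0.40×0.67 + 0.60×0.16 = 0.268 + 0.096 = 0.364. Rounding allows 0.359 to 0.369.
- Share needed for 0.37: (0.37 - 0.16)/(0.67 - 0.16) = 0.21/0.51 = 41%. It is 40% to 42% for effects of 0.365 to 0.375.

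The stated mix does not reproduce -0.37; it falls short by 0.057, or about 15%.

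**Step 2: could it be simulation noise?** The standard error of a median over 1000 data sets with SD 0.11 is about 1.2533×0.11/√1000 = 0.0044. The reported 0.37 lies 13.1 such errors from 0.313 and 1.4 from 0.364. As a cross-check, simulating a baseline-adjusted comparison at assumed correlations of 0.5 to 0.78 gave medians of -0.311 to -0.317 for 30/70 and -0.359 to -0.367 for 40/60.

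**Step 3: alternative meanings of the d values.**

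- Increment: if -0.67 is added to the partial switchers' -0.16, the average is 0.16 + 0.30×0.67 = 0.361 (0.355 to 0.368 with rounding), which is 2.1 Monte Carlo errors from 0.37.
- Rescaling: expressing 0.313 in change-score or residual SD units gives 0.37 at correlations of about 0.64 or 0.53. The standard error on such a scale would be at least √(1/120 + 1/60) = 0.158, not 0.11, and two-sided power about 0.65. This does not rescue the statement.

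**Step 4: what it could mean for power (illustrative only).** Assume two-sided alpha 0.05 and power = Φ(d/SE - 1.96), with three choices of SE at N=180:

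| Basis for SE | SE | d=0.37 (reported) | d=0.313 (30/70) | d=0.364 (40/60) | d=0.361 (increment) |
|---|---|---|---|---|---|
| SD 0.11 already includes attrition | 0.110 | 0.92 | 0.81 | 0.91 | 0.91 |
| SD 0.11 excludes attrition: 0.11×√(1/0.8) | 0.123 | 0.85 | 0.72 | 0.84 | 0.83 |
| Set so that 0.37 gives exactly 0.82: 0.37/(1.96+0.915) | 0.129 | 0.82 | 0.68 | 0.81 | 0.80 |

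Rounding of the SD (0.105 to 0.115) moves the 30/70 figure to between 0.78 and 0.85 in the first row, and between 0.68 and 0.76 in the second.

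**The case against.** The strongest reply is that nothing here shows the power figure to be wrong. That stands. Alpha, sidedness, the analysis model and the correlation borrowed from a previous study are not given, so the simulation cannot be repeated. Taking SD 0.11 as a standard error itself implies baseline adjustment at a correlation of about 0.72 (180 subjects) or 0.78 (144 subjects), values the document does not give. On that basis, with attrition included, 30/70 gives 0.81, close to the stated 0.82. The mix and the power may therefore agree, and only the printed -0.37 may be off.

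The incremental reading is also a fair reply. The sentence does describe the larger effect as relative to partial switchers, and the resulting 0.361 is only 0.003 from the 40/60 value. Against it, the two values are set out in parallel as d, the control is the stated zero point, and the result is called an average of large and small effects. It is possible but unstated.

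A reader might also infer that expecting about 40% and powering on 30% is itself contradictory. It is not: planning on a lower rate than expected is an ordinary precaution. The difficulty is that such a precaution would have produced about -0.31.

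The added enrolment does not settle the matter. With 94 + 92 = 186 participants, 30/70 power moves only to 0.82 (attrition in the SD) or 0.74 (not).

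**Conclusion.** The point holds for the effect size. On the natural reading the stated mix gives -0.313, the paragraph reports -0.37, and neither rounding nor simulation error closes the gap. One of three things is misstated: the 30/70 mix, the -0.37, or the meaning of the d values. The document does not show which. This conclusion needs no assumption about alpha, correlation or model.

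The consequence for power is uncertain. Under the assumptions above, power at 30/70 runs from 0.85 down to 0.68, so the shortfall against 0.82 runs from none to about 14 points. A reader might infer that the trial is underpowered or that 180 subjects are too few. The documents do not support that: at about 40%, or on the incremental reading, the illustrative power is 0.80 to 0.91, and the inputs needed to test the stated 0.82 are not given. This is an inconsistency in the primary sample-size justification that should be corrected, not a demonstrated design failure.

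**What to change.** State in the Sample Size paragraph which mix was simulated, and make the effect and power match it. One of three edits will do:

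1. If 30/70 was intended against control, report the simulation at 30/70 with 20% attrition, with an effect of about -0.31 and the power it gives.
2. If about 40% was simulated, correct the mix and give the 30% result beside it, so that the sensitivity to the switching rate is visible.
3. If -0.67 is an increment over partial switchers, say so in one sentence.

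The cost is one to three sentences, plus a run of the existing simulation wherever the 30/70 result against control has to be reported. N does not change. The downside is a possibly less favourable stated power.

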field and advances science on the widely used practice of EC use for harm reduction among the two largest ethnic minority groups in the US, Latinx and African Americans. Furthermore, this will be among the first studies to determine how uptake of ECs affects cognitive-perceptual factors involved in sustained tobacco use, such as risk perceptions, utility of smoking, self-efficacy to quit, and tobacco dependence among under-represented minority smokers. This study is directly relevant to the NIH's mission to address cancer risk factors and supports the long-term objective to reduce the disease burden of tobacco use. In the current proposal, Latinx ($n=90$) and African American ($n=90$) cigarette smokers will be randomized in a 2:1 fashion to an EC group ($n=60$ per racial/ethnic group; $N=120$) or an assessment-only control group ($n=30$ per racial/ethnic group; $N=60$). Those randomized to EC will receive a 6-week supply of a fourth generation EC starter kit with their choice of liquid flavor from a standard list. Those randomized to assessment only ($n=60$) will not be provided with an EC. Tobacco consumption in both groups will be assessed at weeks 0 (baseline), 2, and 6. Changes in toxic exposure (NNAL, a primary lung carcinogen and the primary outcome) and carbon monoxide (CO) will be measured from baseline to week 6. Planned covariates include study site, gender, income, tobacco dependence score, and mental health symptoms.

Aim 1. To characterize the toxic exposure of cigarette smokers randomized to the EC group compared to cigarette smokers randomized to assessment-only controls

Hypothesis 1: It is hypothesized that toxicant exposure from baseline to week 6 will be significantly lower in the EC group compared to the assessment-only group.

Hypothesis 2: It is hypothesized that change in cigarette consumption in the EC group from baseline to week 6 will be associated with reduction in toxicant exposure from baseline to week 6.

Aim 2. To assess the effects of uptake of e-cigarettes on perceptions of harm and utility of products

It is hypothesized that from baseline to week 6, the EC as compared to control arm a) will have decreased perceptions of harm to their health from current tobacco use, b) will increase positive utility of EC and increase negative utility of cigarette products, and c) will have decreased expectations of the difficulty of quitting cigarette smoking.

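### The week 6 visit window opens on day 14, so it overlaps the week 2 window and conflicts with the protocol's own visit sequence and its six-week, end-of-treatment NNAL endpoint

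*Protocol*

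**What the plan says.** Section VII (Participant Retention) sets both windows relative to baseline. For the earlier visit: "The week 2 visit can be scheduled up to one week before or after the originally scheduled date", which is two weeks after baseline. For the later one: "The week 6 visit can be scheduled up to four weeks before or after the originally scheduled date", which is six weeks after baseline. It then refers elsewhere for detail: "Ripple protocol details the scheduling protocol".

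The Project Summary in section I names the endpoint, "NNAL, a primary lung carcinogen and the primary outcome", and measures its change from baseline to week 6. It also says: "Those randomized to EC will receive a 6-week supply". The Sample Size paragraph powers the primary outcome as an end-of-treatment analysis.

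Section VI describes six weeks of product and places telephone calls at weeks 1 and 4 between the visits. Table 3 in section X keeps that order: week 2, week 4, week 6.

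Under Urine sampling, section VIII collects urine at all three visits, but "only baseline and week 6 urine will be sent for testing". It adds: "In the case of missing week 6 samples, week 2 samples will be sent instead as a method of imputation". Both the time point and the calendar date go into a log: "A urine log will provide the following information for each urine sample".

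**The concern.** The week 6 visit supplies the only planned post-baseline NNAL value. The timing rule for that visit is therefore also the timing rule for the primary endpoint. A tolerance of four weeks on a six-week visit is wide enough to reach back to the nominal date of the previous visit.

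Two things follow:

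- **The protocol treats the same calendar days in two ways.** Under section VIII, a week 2 sample is a fallback, sent only when the week 6 sample is missing and described as imputation. Under section VII, a sample from days 14 to 21 can be an ordinary observed week 6 value.
- **The loss cannot be repaired at analysis.** Table 3 makes week 6 the closing visit, with the exit survey, the cessation referral and collection of used pods, and it lists no further supply. Once that visit is held early, no later urine sample is planned. An analysis plan can flag the date but cannot supply a sample that was never taken.

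Hypothesis 1, the baseline to week 6 contrast in toxicant exposure, is most directly affected. The other baseline to week 6 comparisons in Aims 1 to 3 use the same visit.

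**Working it through.** The protocol gives each window as a nominal date plus or minus a number of weeks. It states no opening or closing day, so there is no printed figure to reproduce. The check is date arithmetic with baseline as day 0.

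**Inputs**
- Week 2 visit: nominal day 14, tolerance 7 days either way (section VII).
- Week 6 visit: nominal day 42, tolerance 28 days either way (section VII).
- Planned product access, e-cigarette arm: 42 days (sections I and VI).
- Week 4 call: taken as day 28 (4 × 7). This is an assumption, because the protocol gives the call only by week.

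**Windows**
- Week 2: 14 − 7 = day 7 to 14 + 7 = day 21.
- Week 6: 42 − 28 = day 14 to 42 + 28 = day 70.
- Overlap: days 14 to 21, which is 21 − 14 + 1 = 8 days.
- The nominal gap between the visits is 42 − 14 = 28 days. The early tolerance equals that whole gap, which is why the week 6 window opens on the nominal week 2 date.

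**Planned product access at the time of sampling (e-cigarette arm only; controls receive no product)**
- Day 14: 14/42 = 33%.
- Day 21: 21/42 = 50%.

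**Can a day 14 visit be in window and in order?** Yes, as far as the two visits go. The week 2 visit may be held on day 7, which leaves 14 − 7 = 7 days to a day 14 week 6 visit, against 28 nominally. The week 4 call does not fit: on day 28 it would come 28 − 14 = 14 days after that visit. Section VII therefore permits a date that the sequence in sections VI and X does not.

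**How much early tolerance is compatible with the protocol's own dates?**

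| Earliest week 6 day | Days early | Share of 42 days | After the week 2 window (day 21)? | After a day 28 call? |
|---|---|---|---|---|
| 14 (as written) | 28 | 33% | No | No |
| 21 | 21 | 50% | No, shares day 21 | No |
| 22 | 20 | 52% | Yes, by 1 day | No |
| 28 | 14 | 67% | Yes, by 7 days | No, same day |
| 29 | 13 | 69% | Yes, by 8 days | Yes |

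Day 22 removes the overlap, but at about half of planned access it does little for an end-of-treatment endpoint, and it still precedes the call. Day 29 is the first day that meets both ordering conditions.

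**Late side.** 70 − 42 = 28 days beyond the planned six-week supply.

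**The case against.** The strongest reply is that the sequence already protects the endpoint. With a week 4 call planned before the week 6 visit, a visit on days 14 to 21 would require the call to be moved well forward or omitted. For a day 14 visit, the week 2 visit must also have been held early or missed. In ordinary running, a visit on day 14 would be the week 2 visit. This is fair, and it means the extreme should not be presented as typical. It does not remove the problem. Section VII calls its windows pre-determined and sets no minimum interval between visits, so the sections disagree and need to be reconciled.

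Second, the Ripple document may hold tighter booking rules. It may, but section VII itself states the four-week tolerance, so a tighter rule there would contradict this text.

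Third, the added harm is limited. The protocol already accepts a week 2 sample when week 6 is missing, and the log records dates, so early samples can be identified. That stands for labelling. It does not help a participant who could have come on time but was booked early, because the on-time sample does not exist.

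Fourth, the tolerance sits under retention and presumably serves it. That supports keeping late visits. It is a weaker reason for allowing the closing visit up to four weeks early.

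A reader might go further and infer that the primary result will be biased, that power is lost, or that participants seen late will have run out of product. The protocol supports none of these. It gives no distribution of visit dates, no time course for NNAL and no record of when pods run out.

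**Conclusion.** The point holds as a conflict within the protocol that reaches the primary endpoint. As written, the week 6 window (days 14 to 70) overlaps the week 2 window (days 7 to 21) on 8 days. It disagrees with the planned week 4 call, and it allows an observed end-of-treatment NNAL value after 33% to 50% of planned product access in the e-cigarette arm. At the other end it extends 28 days past the planned supply, which needs reconciling with an end-of-treatment endpoint but is not a demonstrated error.

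The date arithmetic is certain. How far it matters in practice is not known: these are permitted extremes, no frequency, bias or power effect is claimed, and the Ripple document could narrow the window. The 13-day figure rests on the call staying on day 28. The point is worth fixing because the correction is cheap and must be made before samples are collected. That the protocol has no analysis by actual visit date is not part of it, since that is commonly left to the SAP.

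**What to change.** - **Early side, section VII.** Shorten the tolerance so that the week 6 visit falls after both the week 2 window and the week 4 call: at most 13 days early, that is day 29 or later, if the call stays on day 28. If the call moves, the limit should move with it.
- **Late side, section VII.** Reconcile the upper end (day 70) with the six-week supply and the end-of-treatment endpoint. The limit is for the sponsor to set. Late samples should still be collected.
- **Scheduling document.** Bring section VII and the Ripple document into agreement.
- **Optional.** A sensitivity analysis by actual sample date. The urine log already holds the dates, so it needs no new data. It should stay a sensitivity analysis, because visit timing arises after randomization.

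The cost is a few wording changes and slightly less freedom to schedule the last visit early. No late visit or collected late sample is given up.
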